18. STUDY DEVICE EVENT REPORTING

A Study Device Event refers to the performance of the study device and the occurrence of a deficiency or malfunction as defined in sub-sections below. Device events are to be reported on the Device Event eCRF and submitted to the Sponsor **within 2 business days (Monday through Friday) of first knowledge of occurrence**. Any AE suspected of resulting from a device event must be reported per the required timelines as outlined in **Section 17**.

18.1. Device Deficiency

Device deficiency is defined as inadequacy of a medical device related to its identity, quality, durability, reliability, safety, or performance, such as malfunction, misuse or not observing the IFU, and inadequate labeling.

18.2. Device Malfunction

A malfunction is defined as a failure of a device to meet its performance specifications or otherwise to perform as intended.

18.3. Device Returns

In the event that a device is suspected of deficiency or malfunction, the PI should make every effort to return the device to the manufacturer, Vesper Medical. The PI or designee shall contact Vesper Medical for a return manufacturer authorization number and for additional instructions for the return of potentially biohazardous material.

19. STATISTICAL METHODS AND CONSIDERATIONS

19.1. Introduction

Descriptive statistics for each variable will be calculated which will include the number of observations, mean, standard deviation, median, minimum and maximum for continuous variables and will also include the number and percent of observations for categorical variables.

When the mean is found not to be an appropriate measure of central tendency, alternative statistics will be considered (e.g. median). When the distribution of a variable does not support the use of parametric statistics, nonparametric approaches or data transformations may be implemented. If data transformations are used, they will be specified in the final clinical report.

19.2. Analysis Groups

A subject is defined as ITT and officially enrolled in the study once the DUO Venous Stent System is advanced through the introducer sheath.

Subjects in whom no DUO Stent implant is placed will be exited after 30 days. Subjects in whom at least one DUO Stent implant is placed will be followed for 36 months.

The full analysis set (FAS) are subjects who meet the ITT definition and have data evaluable for the primary endpoints.

The PP population will be defined as ITT subjects with evaluable data that have met the definition for device success, excluding subjects meeting criteria for a protocol violation(s) as outlined in **Section 17.8** and as determined by the Sponsor.

In addition, a SARS-CoV-2 positive population will be defined as:

1. Any documented confirmation of a SARS-CoV-2 positive test result or SARS-CoV-2 positive antibody test (at any approved testing site) from screening through study exit. Subjects will be grouped according to when they became SARS-CoV-2 positive based on the date that testing was performed as compared to the index procedure (i.e., within 30 days, greater than 30 days but within 12 months, greater than 12 months).
2. In the absence of a SARS-CoV-2 test, subjects will be required to complete a COVID-19 questionnaire. Any subject that completes a questionnaire after screening and answers YES to any question on the questionnaire will be included in the SARS-CoV-2 positive population.
3. Regardless of SARS-CoV-2 status or COVID-19 questionnaire results, all adverse events will be assessed by the PI for relatedness to a possible COVID-19 infection by indicating YES, NO, or UNKNOWN.

Any subject that has an adverse event where the PI indicates YES for relatedness will be included in the SARS-CoV-2 positive group.

Due to the unknown but possible risks associated with COVID-19 and hypercoagulability, once a subject is placed in the SARS-CoV-2 positive population, they will remain there regardless of future SARS-CoV-2 test results and or vaccination status. Any subject not meeting the above criteria will be placed in the SARS-CoV-2 Negative population.

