19.7. Handling of Missing Data

A sensitivity analysis to the missing data in the ITT sample will be conducted for both the primary safety and efficacy endpoints in the SARS-CoV-2 negative subset and all subjects. The sensitivity analysis will include a best case, worst case and tipping point analysis. The best-case analysis will impute successes for the missing data. The worst-case analysis will impute failures for missing data. The tipping point analysis starts with the best-case analysis and continues until the worst-case analysis is completed, by increasing the number of missing cases imputed as failures by one in each analysis. The goal of the tipping point analysis is to determine at what point the imputation of

failures causes the statistical evaluation of the endpoint to lose statistical significance. If the worst-case analysis maintains statistical significance, the tipping point analysis is not necessary.

19.8. **Summary of Baseline Demographics, Index Procedure Measurements, and Subject Compliance**

Baseline demographics including at a minimum gender, age, and selected medical history will be summarized for ITT subjects overall and in the SARS-CoV-2 – negative subset for primary safety and for primary efficacy. In addition, angiographic characteristics and measurements, as well as procedure characteristics will be summarized.

Subject follow-up and compliance with the protocol will be reported. The number and percent of subjects enrolled, completing study-required follow-ups, and completing the study will be summarized. The subjects who exit the study early will be summarized along with the reason for early study termination.

19.9. **COVID-19 Statistical Considerations**

Given that COVID-19 has been associated with a hypercoagulable state which has the potential to increase MAE occurrence and decrease patency, the study has been modified to test the primary safety and effectiveness hypotheses in both the SARS-CoV-2 negative subset and all subjects (regardless of SARS-CoV-2 status).

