H₁: Proportion of subjects with freedom from MAE is greater than the (PG) at 30 days, $p_{MAE} > 89\%$

The freedom from MAE proportion will be calculated such that the numerator is the number of subjects in whom a MAE did not occur within 30 days of the index procedure. The denominator is the number of subjects with 30 days of follow-up plus the number of subjects with a MAE prior to 30 days who exited the study prior to 30 days, if any.

Sample Size Rationale: Using PASS 19, a one-sample Exact Test (binomial enumeration), power = 90%, one-sided Type I error controlled at 2.5%, and assumed freedom from MAE of 96.1% with a PG goal of 89%, the required evaluable sample size is 140 subjects.

Primary Statistical Analysis: The primary statistical analysis will be conducted in the FAS subset for the primary safety endpoint overall and in the SARS-CoV-2 negative subset. The primary statistical method is a one-sample exact test comparing the proportion of subjects free from a MAE to the PG using a two-sided $\alpha = 0.05$. The exact two-sided 95% confidence interval for the proportion of subjects free from MAE will be calculated.

The two-sided p-value in the SARS-CoV-2 negative subgroup and all subjects will be calculated and ordered from largest to smallest. If the largest p-value, is statistically significant at $p < 0.05$ then the hypothesis test is statistically significant in both the SARS-CoV-2 negative subset and all subjects. If not, testing continues to the smallest p-value. If the smallest p-value < 0.025 then the hypothesis test is statistically significant in the group for which the smallest p-value is associated with. If the

¹ Razavi MK, Jaff MR, Miller LE. Safety and Effectiveness of Stent Placement for Iliofemoral Venous Outflow Obstruction Systematic Review and Meta-Analysis. Circ Cardiovasc Interv. 2015;8:e002772. DOI: 10.1161/CIRCINTERVENTIONS.115.002772.)

smallest p-value ≥ 0.025 , then the hypothesis test is not statistically significant in either the SARS-CoV-2 negative subset nor all subjects.

Additional Analysis: The evaluation for pooling analyses specified in **Section 19.6** will be completed. If there is missing data for the ITT subjects, the sensitivity to missing data analysis outlined in **Section 19.7** will be completed. Additionally, the primary statistical analysis will be conducted in the per protocol sample overall and in the SARS-CoV-2 negative subset.

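### SARS-CoV-2 negative status depends on results through study exit, so the subset used for the 30-day and 12-month tests drops subjects who first qualify after those endpoints have closed

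*Combined protocol and SAP*

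**What the plan says.** Section 19.2 gives three routes to positive status:

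- a documented positive test or "SARS-CoV-2 positive antibody test (at any approved testing site) from screening through study exit";
- a YES on any questionnaire completed after screening;
- an adverse event that the PI marks as COVID-related.

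None of the three stops at an endpoint window. On exit, the same section says "Subjects in whom at least one DUO Stent implant is placed will be followed for 36 months". On permanence, it says "once a subject is placed in the SARS-CoV-2 positive population, they will remain there regardless of future SARS-CoV-2 test results". The negative population is the remainder: "Any subject not meeting the above criteria will be placed in the SARS-CoV-2 Negative population".

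Section 19.4 lets each primary endpoint be met either in the negative subset or in all subjects, with Hochberg control. Section 19.10 applies this to 30-day safety: "The primary statistical analysis will be conducted in the FAS subset for the primary safety endpoint overall and in the SARS-CoV-2 negative subset". Section 19.11 does the same for 12-month patency. Section 19.9 explains the subset by the possibility that COVID-19 raises MAEs and lowers patency.

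Two passages point towards endpoint-specific subsets. Section 19.2 sorts positives by test date ("i.e., within 30 days, greater than 30 days but within 12 months, greater than 12 months"), and Section 19.8 describes baseline summaries "in the SARS-CoV-2 – negative subset for primary safety and for primary efficacy". Neither is tied to a hypothesis test, and no status cut-off date is given.

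**The concern.** Membership of a confirmatory population should rest on information that belongs to the endpoint being tested. Here a subject free of MAE at day 30 who first tests positive at month 8 leaves the negative subset for the 30-day safety test. One who is patent at 12 months and first tests positive at month 24 leaves the subset for patency, if status is still open when the analysis is run. In general, an infection acquired after an endpoint has closed cannot have affected it, so these exclusions do not serve the reason given in Section 19.9.

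Two things are at stake. The subset test discards valid endpoint data. Membership also comes to depend on what happens after the endpoint: how long a subject is followed and how often that subject is tested. Section 9.2 requires a test at every scheduled and unscheduled visit unless the subject is exempt (for example, vaccinated) or already positive. Section 15.6 reserves unscheduled visits for limb-related events, including reinterventions. Membership can therefore be related to outcome.

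**Working it through.** **Inputs.** Section 19.10: exact one-sample test, PG 89%, assumed freedom from MAE 96.1%, one-sided 2.5%, 140 evaluable, and the Hochberg steps (larger two-sided p below 0.05, otherwise smaller p below 0.025). Section 19.3: attrition of 12.5% at 30 days and 20% at one year. Section 19.11: patency assumptions 0.96/0.87/0.79 and PGs 0.83/0.70/0.66. The documents give no infection rate, so every removal share below is an assumption.

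**Plan's own figure.** The largest number of failures k with P(X ≤ k | n=140, 0.11) ≤ 0.025 is 8 (attained level 0.0240). Power is P(X ≤ 8 | 140, 0.039) = 90.2%, which agrees with the plan. Also 140/0.875 = 160 and 160 × 0.80 = 128.

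**Safety test in the negative subset alone.** The formula is the same, with n = 140 × (1 − share removed after day 30). When only the subset succeeds, Hochberg requires two-sided p < 0.025, that is, one-sided 0.0125.

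| Share removed | n | Failures allowed / power at 0.025 | Failures allowed / power at 0.0125 |
|---|---|---|---|
| 0% | 140 | 8 / 90% | 7 / 82% |
| 20% | 112 | 5 / 73% | 4 / 56% |
| 30% | 98 | 4 / 66% | 3 / 47% |
| 50% | 70 | 2 / 48% | 1 / 24% |

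**Safety met in either population.** This is a simulation of the full Hochberg rule (400,000 runs, true rate 96.1%, removal unrelated to outcome, same MAE rate in positives). With 1% removed, roughly what a day-30 cut-off would do, power is 84.5%. With 20%, 30% and 50% removed it is about 84.2%, 84.0% and 83.3%. The change is 84.5 − 84.2 = 0.3 points up to 84.5 − 83.3 = 1.2 points. Most of the gap from 90.2% is already present at 1% removed, so it comes from the Hochberg step and the discreteness of the exact test rather than from the long status window.

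**Efficacy test in the negative subset alone.** The calculation starts from 128 with an equal disease mix, one-sided 0.025 and an assumed constant monthly hazard h, so the retained share is exp(−h × months).

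- h = 1%: status through 36 months leaves 128 × exp(−0.36) ≈ 89, power 93%. Status to the close of the 12-month window (13 months) leaves 128 × exp(−0.13) ≈ 112, power 97.5%.
- h = 2%: about 62 and 80%, against about 99 and 95%.

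**Type I error for safety.** This is simulated at a true rate of 89%, with an assumed 20% of successes removed.

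| Removal of failures relative to successes | Subset test | Any claim under Hochberg |
|---|---|---|
| 0.5 times | 0.006 | 0.012 |
| equal | 0.016 | 0.016 |
| 1.5 times | 0.040 | 0.027 |
| 2 times | 0.09 | 0.056 |

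The one-sided target is 0.025. Hochberg allows for testing two populations. It does not correct for membership that is related to outcome.

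**The case against.** The strongest reply is that intent is visible. The timing groups match the two endpoint windows, and Section 19.8 names a subset for each endpoint, so perhaps only a linking sentence is missing. That is a fair reading of intent. As written, though, the groups only subdivide positives, and a subject first positive at month 24 is not in the negative population for either test. A confirmatory population should not have to be inferred.

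Three stronger readings are tempting, and the documents do not support them.

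- *The trial's power falls to 48%.* That figure is for the subset test alone. Success needs either population, the all-subjects test is unaffected, and overall power hardly moves when removal is unrelated to outcome.
- *The rule inflates type I error.* It does so only if failures are removed more often than successes. Testing at limb-event visits and the PI's attribution of adverse events could produce that. Early exit of failures would work the other way and is conservative. The direction is not known, and the ratios used above are assumptions. For safety, an implanted subject who survives an MAE has the same planned 36 months as one without.
- *Early enrollees have up to two more years to turn positive before the primary analysis.* That needs an enrollment duration, which the documents do not give. Section 19.5 speaks of analysing the full cohort at 12 months. If status were frozen then, only subjects enrolled earlier could be removed from the patency test by a positive after month 12. The safety part needs no such assumption: each retained subject has by then had about 11 months beyond day 30 in which to qualify.

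It also stands that the date of a test is not the date of infection. A first antibody result after the window may reflect an infection within it. And because vaccinated subjects are exempt from follow-up testing, protocol testing would miss some later positives.

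**Conclusion.** The rule is wrong as written. A subset in which either primary endpoint can be met is defined partly by results obtained after that endpoint has closed, contrary to the plan's own reason for having it. The certain consequence is loss of information in the subset test: safety power of 90% at n=140 against 73%, 66% or 48% for assumed later removal of 20%, 30% or 50%, and 82% against 56%, 47% or 24% at the level needed when only the subset succeeds. The effect on meeting safety in either population is small, about 0.3 to 1.2 points, if removal is unrelated to outcome. Error inflation is possible but not established. It rests on assumed removal ratios and could equally turn out conservative. The point is worth settling before analysis because the subset is confirmatory and the correction is easy; it does not show that the study is underpowered or that its error rate is uncontrolled.

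**What to change.** In Section 19.2, define the negative subset separately for each endpoint, building on the timing groups already there.

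- **Primary safety:** count as positive only status dated up to day 30, or up to the close of the 30-day visit window. Choose one in advance; the visit, with its DUS and SARS-CoV-2 test, may fall up to 14 days late.
- **Primary efficacy:** count only status dated up to the close of the 12-month visit window, with the same cut-off for every subject. Do not shorten it to the date of patency loss, because membership would then depend on outcome.
- **All routes:** apply the cut-offs to test or antibody results, questionnaires and PI-attributed adverse events alike.
- **Late antibody results:** state in advance how a first positive antibody result after the cut-off is handled.
- **Data-cut:** fix a status date for the primary analysis.
- **Sensitivity:** report the through-exit definition alongside.

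The cost is SAP wording. Section 19.2 already groups positives by test date, and no new data are needed. The downside is that some subjects infected before a cut-off but first detected after it will stay in the negative subset.

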Stent placement has a high technical success rate and is effective at restoring patency.¹⁷ Technical success of stent placement has been reported to be 84-93% in chronic postthrombotic iliac vein obstruction.¹⁸ Clinical improvement appears to be long lasting.¹⁹ Neglen reported on a group of 982 subjects with chronic nonmalignant obstructive lesions of the femoroiliocaval vein that were stented under IVUS guidance. Primary, assisted primary and secondary patency rates of 57%, 80%, and 86% were achieved at 6 years in thrombotic disease while nonthrombotic rates were 79%, 100%, and 100%, respectively.²⁰ Other smaller studies have reported similar results.^{21,22,23,24,25,26} More recent data reported primary, assisted primary, and secondary patency rates of 93%, 96%, and 100%, respectively,

at 1 year, in the first 30 subjects treated with the Veniti Vici stent²⁷ and 85% primary patency in the first 20 subjects treated with the Zilver Vena stent.²⁸

Adverse Events (AEs) associated with venous stenting have been minimal. The most common complications include early (<30 days) and late thrombosis (1.5-3% and 5%, respectively). Mortality is low, reported at 0-1%.²⁹ Extension of the stent into the IVC is associated with contralateral iliac vein occlusion 1% of the time. However, failure to extend the stent into the IVC when needed may result in an ipsilateral restenosis or occlusion rate of 36%.³⁰ Absolute contraindications listed for ilio caval stenting include uncorrectable coagulopathy and local or systemic infection.³¹

In summary, stenting in chronic ilio caval obstruction is safe and effective. Excellent long-term results with respect to revascularization and symptom relief have been achieved. Recanalization to treat venous claudication with venous stents suggests the highest probability of success.^{32,33}

The Vesper DUO™ Venous Stent System is a new purpose-built stent system that will be studied for use in treating iliac and common femoral vein obstructions due to either nonthrombotic or postthrombotic etiology.

4.2. **Report of Prior Investigations**

This is the first investigation of the DUO Venous Stent System in humans.

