Severe: A severe adverse event is an AE that results in significant symptoms that prevent normal activities and may require hospitalization or invasive intervention.

The relationship of the AE to the device or study device procedure will be classified according to the following criteria:

Unrelated: The AE is clearly not related to the study device or study device procedure.

Possibly: Signs or symptoms of the AE may be related to the study device or study device procedure and/or the natural disease process or other injury/illness.

Definitely: The AE is clearly related to the study device or study device procedure. Signs and symptoms could not reasonably be related to the natural disease process or other injury or illness.

Unknown: Unable to determine the relationship between the study device, study device procedure, natural disease process and/or other injury/illness.

In addition, all AEs will be assessed and recorded in the eCRF by the PI or Sub-I for relatedness to COVID-19 by indicating:

- Yes, related to COVID-19
- No, not related to COVID-19
- Unknown

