19.4. Study Success

The study will be considered a success if the primary safety endpoint is met in either the SARS-CoV-2 negative subset or all subjects and the primary efficacy endpoint is met in either the SARS-CoV-2 negative subset or all subjects. The Type I error for testing in both the SARS-CoV-2 negative subset and all subjects will be controlled using the Hochberg correction.

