The performance goals for both primary safety and primary effectiveness were established based on research in a pre-COVID-19 era and therefore do not account for potential increases in MAEs or decreases in patency associated with SARS-CoV-2 or COVID-19. For each of the hypothesis tests, the current plan is to use the same performance goal in all subjects and in the SARS-CoV-2 negative subgroup given that the potential effects due to SARS-CoV-2 are not well understood. This decision will be revisited prior to analysis of the study data. In the event that additional information becomes publicly available regarding SARS-CoV-2, as related to the VIVID study primary endpoints, we may summarize the major event rate and primary patency in the subject population without and with SARS-CoV-2, and if possible, further based on the extent of COVID-19 illness. Should this information suggest that it may be reasonable to lower the performance goal for the all subject cohort, negotiation with FDA will be pursued given the FDA guidance document, “Statistical Considerations for Clinical Trials During the COVID-19 Public Health Emergency” dated June 2020.

19.10. **Primary Safety Objective**

Subjects Included the Analysis: Subjects who meet the ITT definition.

Endpoint: The primary safety endpoint is freedom from major adverse events (MAEs) at 30 days post index procedure evaluated per subject. MAEs are defined in **Section 6.1** Primary Endpoints.

Performance Goal: Disease state specific PGs were calculated from the point estimates for major bleeding, pulmonary embolism and peri-procedural mortality from Razavi et al¹ converted to freedom from estimates and application of a 10% non-inferiority margin. For example, the expected freedom from the combined primary safety event for nonthrombotic subjects is $100 - (0.3 + 0.2 + 0.1) = 99.4\%$. Therefore, the PG for the nonthrombotic group is $99 - 10 = 89\%$. The same calculation for the acute-thrombotic group results in an 87% PG, $87\% = 100 - (1.1 + 0.9 + 0.7) - 10$. Lastly, the PG for chronic postthrombotic is $88\% = 100 - (0.9 + 0.6 + 0.3) - 10$. Given the similarity of the disease-state specific PGs, it was determined that a disease state specific goal was not necessary. A PG of 89% was adopted for the study in both the SARS-CoV-2 negative subset and overall.

Hypothesis and Performance Goal:

H₀: Proportion of subjects with freedom from MAE (p_{MAE}) is less than or equal to the (PG) at 30 days, $p_{MAE} \leq 89\%$

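### An unreviewed site rating of COVID-19 relatedness can move an endpoint failure out of the SARS-CoV-2 negative subset, which can meet each primary endpoint alone

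*Combined protocol and SAP*

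**What the plan says.** Section 19.2 gives three routes into the SARS-CoV-2 positive population: a positive virus or antibody test, a yes on the questionnaire used when there is no test, and a site rating. On the third it says: "Any subject that has an adverse event where the PI indicates YES for relatedness will be included in the SARS-CoV-2 positive group". This route applies whatever the test or questionnaire shows. Once subjects are classed as positive, "they will remain there regardless of future SARS-CoV-2 test results and or vaccination status". Everyone else forms the negative subset.

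Section 17.1 says who rates: "all AEs will be assessed and recorded in the eCRF by the PI or Sub-I for relatedness to COVID-19". A NO or UNKNOWN moves nobody. No section exempts an MAE or a loss of patency from the rating.

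Section 19.4 states: "The study will be considered a success if the primary safety endpoint is met in either the SARS-CoV-2 negative subset or all subjects". It says the same for efficacy. Sections 19.10 and 19.11 apply Hochberg to the two populations: "If the smallest p-value < 0.025 then the hypothesis test is statistically significant in the group for which the smallest p-value is associated with".

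Sections 21.7.2 and 21.8 have the CEC and the Medical Monitor consider relation to the device or procedure. Neither mentions relation to COVID-19. Section 19.2 also bands positives by time ("within 30 days, greater than 30 days but within 12 months, greater than 12 months"), but no section links the bands to the hypothesis tests.

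**The concern.** Membership of a confirmatory population depends on a judgement made after treatment, in a single-arm, non-blinded trial, and possibly about the outcome itself. Section 19.9 links COVID-19 to hypercoagulability, more MAEs and lower patency. A PE or a new stent thrombus therefore invites a YES in a way that an uneventful course does not. Other MAE types are unlikely to be rated YES, and a silent stenosis may never be recorded as an adverse event.

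Hochberg handles the testing of two populations provided each p-value is valid. The negative-subset p-value is valid only if failures are not moved out more often than successes. The all-subjects test is unaffected, but Section 19.4 does not require it to pass, so any bias in the subset reaches the study-success claim.

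**Working it through.** **Plan's own figure.** Section 19.10 gives 140 evaluable subjects, a goal of 89%, an assumed rate of 96.1%, 90% power and one-sided 2.5%. The exact binomial rule at n = 140 passes with at most 8 failures. P(at most 8 failures | 89%) = 0.0240 and P(at most 8 failures | 96.1%) = 0.902. Both agree with the plan.

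**Worked example.** Two-sided exact p-values against 89%. Section 19.10 does not say how the two-sided p is formed, so two conventions are shown.

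| MAE-free / N | Twice the upper tail | Probability ordering |
|---|---|---|
| 131/140 (9 MAEs, all subjects) | 0.0964 | 0.1031 |
| 131/138 (two rated YES) | 0.0244 | 0.0281 |
| 131/137 (three rated YES) | 0.0103 | 0.0091 |

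Nine MAEs fail overall. With no other positives, two ratings pass the 0.025 threshold under the first convention only, and three pass under both. If 20% of subjects are already out for other reasons, 140 × 0.8 = 112 remain, with 9 × 0.8 ≈ 7 MAEs. Two ratings then leave 5 MAEs in 110 (doubled tail p = 0.029, fail). Three leave 4 in 109 (p = 0.011, pass).

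**Share of MAEs that could plausibly be rated YES.** Section 4.1 gives early thrombosis of 1.5-3%. The rates in Section 19.10 were "calculated from the point estimates for major bleeding, pulmonary embolism and peri-procedural mortality". Read in that order they are 0.3/0.2/0.1 (nonthrombotic), 1.1/0.9/0.7 (acute thrombotic) and 0.9/0.6/0.3 (chronic postthrombotic).

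Share = (thrombosis + PE) / (thrombosis + PE + bleeding + death).

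- Lowest, acute thrombotic: (1.5 + 0.9) / (1.5 + 0.9 + 1.1 + 0.7) = 2.4/4.2 = 57%.
- Highest, nonthrombotic: (3 + 0.2) / (3 + 0.2 + 0.3 + 0.1) = 3.2/3.6 = 89%.

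These are upper estimates, because no rates are given for venous injury, amputation or embolization. Using them at an 11% MAE rate is a further assumption. If 20% of PE/thrombus subjects are rated YES, then 0.20 × 57% to 0.20 × 89% = 11-18% of MAE subjects move. At 30%, the upper end is 0.30 × 89% = 27%.

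**False success for safety.** True rate 89%, N = 140, 20% test-positive regardless of outcome, doubled-tail p. Success means both p < 0.05 or the smaller p < 0.025. Let q be the share of otherwise-negative failures moved by rating and r the share of otherwise-negative successes moved. Subset failures ~ Bin(F, 0.8(1−q)) and subset successes ~ Bin(140−F, 0.8(1−r)), with F ~ Bin(140, 0.11).

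| q | r = 0 | r = 5% | r = 10% |
|---|---|---|---|
| 11-18% | 2.6-3.6% | 2.1-2.9% | 1.7-2.3% |
| 27% | 6.2% | 4.9% | 3.7% |

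With q = r = 0 the result is 1.6%. With q = r = 20% it is also 1.6%.

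**False success for efficacy.** N = 128, equal disease mix, true patency at the disease-specific goals, Z-test and null variance of Section 19.11, 20% test-positive (simulated).

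| q | r = 0 | r = 5% | r = 10% |
|---|---|---|---|
| 10% | about 3.6% | about 2.6% | about 1.8% |
| 20% | about 8.5% | about 5.9% | about 3.9% |

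With q = r = 0 the result is about 1.8%. With q = r = 20% it is about 1.9%.

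**If every YES is correct.** Assume freedom from MAE of 89% in uninfected and 80% in infected subjects, 20% test-positive, and every MAE in an undetected infected subject rated YES. False safety success is 1.8% with 10% undetected infection and 4.37% with 20%. Accurate ratings can inflate because infected subjects with an MAE leave while infected subjects without one stay.

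**The case against.** The strongest reply is that event-free subjects will be moved too. The rating covers every type of adverse event through study exit, and fever or respiratory illness is a natural YES. This stands. It lowers the inflation materially, and at q = 11-18% with r = 10% the error stays below 2.5%.

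Second, true infections are mostly caught by other routes. Entry screening and follow-up testing do limit the problem. A reader might infer that the testing waivers in Section 9.2 leave antibody-positive subjects undetected in the negative subset. They do not, because a positive antibody test from screening onward already makes a subject positive under Section 19.2. The waiver for vaccinated subjects does leave a gap. Section 19.2 calls for a questionnaire when there is no test, but Section 9.2 describes it at follow-up only for unavailable tests, so coverage of vaccinated subjects is unclear.

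Third, a reader might infer that nobody will ever review the rating. The documents support only that no review is stated in them, since CEC methods are deferred to a charter that is not included.

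Fourth, the CEC could make the rating without knowledge of endpoint status, which would preserve the aim of comparing a COVID-free group with pre-COVID goals. That is a fair alternative in principle. It is hard to carry out when the event being rated is itself the endpoint event.

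**Conclusion.** The weakness is real but conditional, and should be fixed. As written, the rule lets an outcome-linked, unblinded rating decide who is in a population that can carry each primary endpoint, and Hochberg offers no protection against that.

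The size is uncertain. All rating shares and the 20% test-positive share are assumptions. Over the cases in the tables, false safety success runs from 1.7% to 6.2% and false efficacy success from about 1.8% to 8.5%, against a nominal 2.5%. Efficacy values near the top require many patency failures to be recorded as adverse events and rated YES.

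Three stronger readings are not supported. The documents do not show that type I error is inflated, only that nothing prevents it. Two ratings do not generally overturn a failed safety result: that needs no other positives and the doubled-tail convention. Nor does the concern depend on mistaken or dishonest ratings, as the 4.37% case shows.

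**What to change.** In Section 19.2:

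1. Remove the site rating from membership of the confirmatory negative subset. Keep it as a descriptive field or for a sensitivity analysis.
2. Count a subject as positive for an endpoint only on a test or questionnaire up to that endpoint's cut-off, using the existing time bands: 30 days for safety, close of the 12-month window for efficacy. State how a test at a 30-day visit held on days 31-44 counts. That visit is scheduled for everyone, but a subject who has died cannot attend, so it is not fully neutral to outcome.
3. Add a sensitivity analysis in which a positive first found at or after the endpoint failure, or at an event-triggered visit, does not move the subject. State that changes 1 and 2 do not remove bias from event-triggered testing. If 25% or 30% of failures test positive against 20% of other subjects, residual false success is 2.01% or 2.71% for safety and 2.65% or 4.44% for efficacy. The sensitivity analysis exposes this bias but does not correct the confirmatory test.
4. Tabulate the positive population by criterion and endpoint status.

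In Section 19.10, state how the two-sided exact p-value is formed.

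The cost is wording, one sensitivity analysis and one table, with no new data. The downside is that a few truly COVID-related failures without a positive test or questionnaire stay in the negative subset, which is the conservative direction.
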